Physical examination, venipuncture/IV placement, EKG, lab data collection and analysis: Subjects will receive a comprehensive medical history assessment, physical examination, EKG, and lab testing to ensure good physical health status and eligibility. These are routine medical procedures and should add no risks other than those normally associated with these procedures. Study doctors and/or nurse practitioners will assess the EKG and screening laboratory blood work. If any abnormal findings occur, they will provide appropriate medical advice. Potential participants who are excluded from the study due to medical reasons, or those who are in immediate need for medical or psychiatric attention, will be referred to the appropriate facilities at Yale New Haven Hospital so they can receive the clinical care needed to address their condition. Subjects will be exposed to the risk of venipuncture/IV placement that is routinely done in the HRU at the YNHH. Risks associated include: local bruising, hematoma, or infection. If this occurs, appropriate treatment will be provided immediately. On extremely rare occasions, a blood clot or infection might occur, and if this occurs, subjects will be treated at the HRU, which is fully staffed with nursing specialists and medical personnel. These risks are mitigated by the use of research HRU nurses who have extensive experience in venipuncture and IV catheterization. Transient vasovagal symptoms, e.g., nausea, sweating, and lightheadedness may also occur during IV catheter placement. Careful efforts to maintain confidentiality have been effective in previous research, and only patients' code numbers will be recorded on forms to protect confidentiality. Efforts to protect confidentiality are further detailed below.

Oral glucose tolerance test (OGTT): The OGTT is a commonly used outpatient test for diagnosis of type 2 diabetes. It is not associated with any specific adverse effects. Occasionally, some patients may experience mild nausea or GI discomfort following drinking the 75 gram glucose drink; however, this typically resolves after eating food.

HIC 2000030749

Microneurography: The risk of microneurography is a peroneal paresthesia for 2-10 days following the experiment. The incidence of paresthesia is reported to be less than 10%, in less than 1% of all subjects paresthesia can persist for up to two months. Paresthesia resolves spontaneously. Microneurography can occasionally be painful, but this is very unusual.

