Two weeks after visit 4, participants will be asked to return for a separated visit for measurements of SNS activity at rest and after intake of liquid meal. Participants will undergo similar procedures described on visit 4. However, MSNA will be obtained after MMT. The participants will come in the morning (~9am) and will be asked to fast for 10-hour and to maintain their regular exercise routine. A nurse will insert an intravenous (IV) catheter and subjects will ingest a liquid meal (65% CHO, 20% fat, and 15% protein, equal to 40% of daily energy expenditure, per ~16 ounces) to be prepared by the Metabolic Kitchen. Measurements of HR, BP, and EKG (beat-to-beat) will be obtained during the procedure. An intravenous catheter will be inserted into a forearm vein for blood sampling. Following the instrumentation period, resting HR, pulse interval (PI), BP, and MSNA will be recorded for 10 minutes. Following these measurements, plasma will be taken for measurements of insulin, glucose, free fatty acids, norepinephrine, and epinephrine levels. Approximately 40 mL of blood will be drawn at this visit.

HIC 2000030749

Participants will be asked to maintain their regular exercise routine. The order of SNSA Fasting and MMT visits (visits 4 and 5) will be randomized. All study visits will be conducted within an 8-week period (including the two PET and SNSA scans).

Schematic figure of the visits and procedures to be done. The order of the PET scans will be randomized.

Abbreviations: BP=blood pressure, EKG=electrocardiogram, HR=heart rate, MSNA=Muscle sympathetic nerve activity, SNSA=Sympathetic Nervous System Activity

Method of Assignment/Randomization- The order of the PET scan visits 2 (PET-CT Fasting) and 3 (PET/CT-MMT) will be randomly assigned (with a 50% chance of being assigned to each visit). SNSA visits 4 (fasting) and 5 (MMT) will be also be also be randomized (with a 50% chance of being assigned to each visit).

PET and MSNA visits do not need to occur in sequence, i.e. PET scans can occur before or after the MSNA.

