Unanticipated Problems Involving Risks to Subjects or Others (UPIRSOs) may be medical or non-medical in nature, and include – but are not limited to – serious, unexpected, and related adverse events and unanticipated adverse device effects. Please note that adverse events are reportable to the IRB as UPIRSOs only if they meet all 3 criteria listed above.

These UPIRSOs/SAEs will be reported to the IRB in accordance with IRB Policy 710, using the appropriate forms found on the website. All related events involving risk but not meeting the prompt reporting requirements described in IRB Policy 710 should be reported to the IRB in summary form at the time of continuing review. If appropriate, such summary may be a simple brief statement that events have occurred at the expected frequency and level of severity as previously documented. In lieu of a summary of external events, a current DSMB report can be submitted for research studies that are subject to oversight by a DSMB (or other monitoring entity that is monitoring the study on behalf of an industry sponsor).

7. Plan for reporting adverse events to co-investigators on the study, as appropriate the protocol's research monitor(s), e.g., industrial sponsor, Yale Cancer Center Data and Safety Monitoring Committee (DSMC), Protocol Review Committee (PRC), DSMBs, study sponsors, funding and regulatory agencies, and regulatory and decision-making bodies.

For the current study, the following individuals, funding, and/or regulatory agencies will be notified:

- All Co-Investigators listed on the protocol.
- National Institute of Health

1 Other Data Safety Monitoring Board (DSMB) or Committee (DSMC): The Yale PET Center's internal Data Safety Monitoring Board, composed of the Directors of the PET Center, also meets to review any adverse events on a monthly basis.

1 Yale New-Haven Radiation Safety Committee (if applicable)

Yale University Radiation Safety Committee (if applicable)

The principal investigator [name] [name] will conduct a review of all adverse events upon completion of every study subject. The principal investigator will evaluate the frequency

HIC 2000030749

and severity of the adverse events and determine if modifications to the protocol or consent form are required.

Research staff will call subject 1-3 days after the PET scan to check in and address any adverse events that may have arisen post PET scan.

The study will be stopped if either of the following occur:

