6.3.5 On Study Visits

Screening

- Consent
- Urine Pregnancy test for women of child-bearing potential
- Height and Weight using Tanita Scale
- EKG
- IV Insertion and OGTT
- Blood draw for anemia, kidney and liver function and thyroid test and diabetes
- Physical & Medical History
- DXA Scan

Visit 2 & 3 PET Scans

- Subject will arrive to PET Center, fasted
- Urine Pregnancy Test for women of child bearing potential
- Urine Drug Screen
- A-line and IV insertion
- Mixed Meal Test on Visit 3
- A low dose CT scan will be completed immediately before or after each PET scan.
- Up to 3-4 hour PET scan
- Collection of Blood Sampled during PET scan
- Light Lunch given to subject after PET Scan

Visits 4 & 5

HIC 2000030749

- Subject will arrive fasted to the Pierce Laboratory for measurements SNS activity
- Urine Sample Collection
- Collection of Weight
- Collection of the following: Microneurography, BP, HR
- EKG
- IV Insertion
- Blood Sample
- Measurement of skin blood flow
- Sympathetic Nervous System Activity (SNSA) measurement

Visit 1: Screening Visit
 
 -Review of Consent Form -Physical and Medical history review -Pregnancy Test (females) -EKG -Blood Work -OGTT -Body Composition 
 -Tanita Scale -DXA Scan 	
Visit 2: Whole body PET/CT
 
Imaging
 
Fasting Visit
 
 - Urine Pregnancy Test (females) - Urine Drug Screen - [¹¹C]MRB - Low dose CT scan and PET scan - Norepinephrine levels (serum) 	
Visit 4: SNSA Visit – Fasting
 
 - BP, HR, PI, HR variability - EKG - MSNA
	
Visit 3: Whole body PET/CT
 
Imaging
 
Mixed Meal Test Visit
 
 - [¹¹C]MRB - Urine Pregnancy Test (females) - Urine Drug Screen - Ingestion of mixed meal - Measurement of Energy Intake - Low dose CT scan and PET scan - Norepinephrine levels (serum) 	
Visit 5: SNSA Visit - Mixed Meal Test
 
 - Ingestion of mixed meal - BP, HR, PI, HR variability - EKG - MSNA

Abbreviations: BP=blood pressure, EKG=electrocardiogram, HR=heart rate, MSNA=Muscle sympathetic nerve activity, SNSA=Sympathetic Nervous System Activity

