6.3.6 End of Study and Follow-up

Follow Up Procedures:

A member of the study team will reach out to the subject 1-2 weeks upon study completion for a brief follow-up telephone call. During this phone call, the subject will be asked how they are feeling since completing the study assessments and if they have any questions or concerns.

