7.12 Data Safety Monitoring Plan

The principal investigator [name] [name]. will conduct a review of all adverse events upon completion of every study subject. The principal investigator will evaluate the frequency and severity of the adverse events and determine if modifications to the protocol or consent form are required.

Research staff will call subject 1-3 days after the PET scan to check in and address any adverse events that may have arisen post PET scan.

The study will be stopped if either of the following occur:

1) If 1 or more subjects experiences a serious adverse event (SAE), which is considered by the investigator to be possibly or probably related to the radiotracer.

HIC 2000030749

2) If 2 or more subjects experience AEs of severe intensity, which are considered by the investigator to be possibly or probably related to the radiotracer and of clinical concern.

After review of the safety data, SAEs and AEs confirmed to have been related to the radiotracer will be reported to the FDA and the appropriate regulatory committees at Yale. The study will be placed on hold until a determination is made as to whether the study may continue as written, if modifications are needed, or if the study will be discontinued.

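### The early adverse-event call follows only the PET scan; microneurography, the one procedure with stated complication rates, has no early call and no follow-up to resolution

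*Combined protocol and SAP*

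**What the plan says.** **Early contact.** Section 6.2.3 provides for it and attaches it to imaging: "Research staff will call subject 1-3 days after the PET scan to check in and address any adverse events". Section 7.12 does the same: "Research staff will call subject 1-3 days after the PET scan". Both limit its purpose to events arising after that scan.

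**Stated risks.** For the tracer, section 3.2.1 says that no adverse effects have been reported, while allowing for a rare reaction. For microneurography the same section is specific: "The risk of microneurography is a peroneal paresthesia for 2-10 days following the experiment". It then says "The incidence of paresthesia is reported to be less than 10" per cent, and that "in less than 1% of all subjects paresthesia can persist for up to two months". It adds that the symptom goes away by itself.

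**Exposure.** Each participant has microneurography at both sympathetic nervous system activity (SNSA) visits, Visits 4 and 5. Section 5.1 sets the interval: "Two weeks after visit 4, participants will be asked to return for a separated visit".

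**What is asked at those visits.** The Visit 4 and 5 list in section 6.3.5 includes "Collection of the following: Microneurography, BP, HR", with EKG, blood and urine samples, weight and skin blood flow. It has no symptom question.

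**Last contact.** Section 6.3.6: "A member of the study team will reach out to the subject 1-2 weeks upon study completion for a brief follow-up telephone call". The call asks in general terms how the subject has felt and whether there are questions or concerns.

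**The concern.** Active enquiry is aimed at the procedure with no reported adverse effects, and not at the one with a known complication. Three things follow if the plan is carried out exactly as written.

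- A typical episode of paresthesia is over before anyone is scheduled to hear of it, so onset, severity and duration are recalled and not observed. Section 6.2.3 wants relatedness judged by a clinician who examines the participant and weighs timing, which is hard to do once the episode has passed.
- A participant with continuing symptoms can reach the second electrode insertion without a listed question about them.
- A prolonged case noticed at the final call has no planned next step.

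What is at stake is participant safety and the completeness of the adverse-event record. The investigator uses that record, under 6.2.3 and 7.12, to decide whether the protocol or consent form must change.

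**Working it through.** The plan gives no figure of its own on this point, so there is none to reproduce. The check sets the contact schedule against the stated course of the complication.

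**Inputs**
- 40 participants with two microneurography sessions each (5.3.1, 5.1)
- Paresthesia: under 10%, 2-10 days; under 1% of subjects, up to two months, taken as 60 days (3.2.1)
- Visits two weeks apart (5.1)
- Final call 7-14 days after study completion (6.3.6)
- PET and SNSA visits may come in either order (5.1)

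**1. Expected cases at the upper bounds**
- Any paresthesia: 40 × 0.10 = 4
- Prolonged: 40 × 0.01 = 0.4
- Chance of at least one prolonged case: 1 − 0.99^40 = 0.331

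The 1% is stated per subject; the 10% has no stated unit. If both applied per procedure, with 80 procedures, the maxima would be 80 × 0.10 = 8 and 80 × 0.01 = 0.8, and the chance of at least one prolonged case 1 − 0.99^80 = 0.553.

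**2. Typical episode against the next contact**

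If symptoms start on the day of the session:

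| Contact | Shortest episode (ends day 2) | Longest typical episode (ends day 10) |
|---|---|---|
| Call at day 1-3, as after PET | running, or over by at most 3 − 2 = 1 day | running |
| Final call at day 7 | over by 7 − 2 = 5 days | running, 10 − 7 = 3 days left |
| Visit or final call at day 14 | over by 14 − 2 = 12 days | over by 14 − 10 = 4 days |

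**3. Prolonged episode against the last contact**

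Number the four PET and SNSA visits k = 1 to 4 at two-week spacing. The final call comes 14 × (4 − k) + 7 to 14 × (4 − k) + 14 days after visit k. The days left of a 60-day course are 60 minus that.

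| Position of the session | Final call (days after session) | Days left of a 60-day course |
|---|---|---|
| 4 | 7-14 | 46-53 |
| 3 | 21-28 | 32-39 |
| 2 | 35-42 | 18-25 |
| 1 | 49-56 | 4-11 |

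For the second session this gives 46-53 days if the SNSA visits come last and 18-25 if they come first. For the first session it gives 32-39 and 4-11. Mixed orders fall on the same rows. In every position a course of the full stated length runs beyond the last planned contact.

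**4. PET visit after an SNSA visit**

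If a PET visit comes next, two weeks later, its call falls at day 14 + 1 = 15 to 14 + 3 = 17 after microneurography. That is later than the visit itself, and the call is directed at post-PET events.

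**The case against.** The best case for the plan is that the symptom is expected, disclosed and said to resolve unaided, and that safeguards exist. Section 3.2.1 limits search time to under 60 minutes, forbids reusing a nerve site, and requires experienced operators and inspected, sterile, single-use electrodes. Section 6.2.3 has adverse events monitored for each subject, attributed, and reviewed when each subject finishes. Treatment and referral for injury are covered in 3.2.1 and 6.5.7. At the second SNSA visit the participant spends a long time with staff who could well hear of leg symptoms. The PET call is not misplaced either: those visits include an arterial line as well as the tracer. Consent pages are not in the public file, and microneurography also runs under a separate approved protocol that cannot be seen here, so self-report instructions may exist.

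Some of this stands. The PET call should stay. The rates are upper bounds, so the counts are maxima. The final call can pick up a persistent case and, if made at day 7, one near the long end of the typical range. An instruction elsewhere to report symptoms cannot be excluded.

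It does not close the gap. The microneurography precautions prevent injury; they do not look for it afterwards. The attribution, review and referral text deals with events already known and gives no time or question for eliciting them after an SNSA visit. Long contact is not a listed check before a second insertion. Self-report would not replace the active enquiry that the plan already provides after PET.

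**Conclusion.** The concern holds, as a minor point. The documents tie early adverse-event enquiry to PET alone, leave microneurography to a contact at about day 7-14, list no symptom check before the second insertion, and plan no follow-up to resolution. At the stated upper bounds, read per subject, up to 4 of 40 participants would have paresthesia and an expected 0.4 at most a prolonged course. The timing results assume two-week spacing throughout, onset on the day of the session and two months taken as 60 days. The weakness lies in asking early and following up, not in the review of recorded events. No endpoint, analysis or sample-size figure depends on it.

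**What to change.** - In 6.2.3 and 7.12, make the 1-3 day call follow each PET visit and each SNSA visit, and widen its purpose to events after either procedure.
- Ask specifically about leg numbness or tingling at the call after each SNSA visit, before electrode insertion at the second SNSA visit (add to the list in 6.3.5), and at the final call in 6.3.6.
- State that anyone with open symptoms is contacted again until they resolve, with the end date recorded.

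The cost is 40 × 2 = 80 short calls by staff who already make the PET calls, one added question at an existing visit and at the final call, and a few repeat calls for symptomatic participants. Only protocol wording changes.

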Microneurography. The likelihood of the occurrence of symptoms following microneurography will be minimized by the following certain procedures. First, few problems or symptoms are reported in laboratories whose microneurographers have received training from individuals with a documented record of success and safety. [name] or [name] will perform all microneurography studies. [name] is a highly qualified microneurographer in the laboratory with over two years' experience, and [name] has performed microneurography in her laboratory for 10 years, and this will reduce the risk of occurrence of symptoms following the experiment. The time spent searching for a nerve fascicle within the peroneal nerve will be limited to $<$ 60 min. No nerve site will be sampled more than once. The recording electrodes are inspected under a dissecting microscope to ensure electrode tip integrity (those electrodes found with damaged tips are not used) and each recording electrode will be used only once for intraneuronal recording. Placement of the electrodes and positioning in the common peroneal nerve are performed under sterile conditions. Metal microelectrodes are steam sterilized at Yale New Haven Hospital before use. The site of electrode placement is cleaned with alcohol and only investigators wearing sterile gloves handle the sterile microelectrodes. Following these simple guidelines, the risk of occurrence of symptoms following microneurography will be small. Microneurography studies are conducted at the Pierce Laboratory.

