6.2.3 Adverse Events Definition and Reporting

1. Personnel responsible for the safety review and its frequency:

The principal investigator, [name] [name] will be responsible for monitoring the data, assuring protocol compliance, and conducting the safety reviews at the specified frequency, which must be conducted at a minimum of every 6 months (including when reapproval of the protocol is sought). During the review process, the principal investigator will evaluate whether the study should continue unchanged, require modification/amendment, or close to enrollment. Either the principal investigator, the HIC, or the RSC have the authority to stop or suspend the study or require modifications.

HIC 2000030749

2. The risks associated with the current study are deemed greater than minimal for the following reasons: (choose those that apply)

The total amount of radiation in this study is from up to 3 low dose CT scans - used to optimize the PET scan – and up to 3 injections of radioactive material (20 mCi), [11C]MRB and from a low dose CT scans used to help obtain the PET images and the DXA scan .

The average yearly background radiation in the United States is about 0.3300 mrem. The amount of additional radiation from participating in this study is about 2.307 rem. This is equal to about 7.69 years worth of natural radiation.

The amount of radiation subjects will receive in this study is below the dose guidelines established by the RIDC guidelines for research purposes. This guideline sets an effective dose limit of 5 rem per year.

Adverse effects of the radiopharmaceuticals in this study have not been reported. However, the possibility exists for a rare reaction to any of the substances or procedures to which a subject is exposed.

3. Attribution of Adverse Events:

Adverse events will be monitored for each subject participating in the study and attributed to the study procedures / design by the principal investigator [name] [name], according to the following categories:

- a.) Definite: Adverse event is clearly related to investigational procedures(s)/agent(s).
- b.) Probable: Adverse event is likely related to investigational procedures(s)/agent(s).
- c.) Possible: Adverse event may be related to investigational procedures(s)/agent(s).
- d.) Unlikely: Adverse event is likely not to be related to the investigational procedures(s)/agent(s).
- e.) Unrelated: Adverse event is clearly not related to investigational procedures(s)/agent(s).

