- 1) If 1 or more subjects experiences a serious adverse event (SAE), which is considered by the investigator to be possibly or probably related to the radiotracer.
- 2) If 2 or more subjects experience AEs of severe intensity, which are considered by the investigator to be possibly or probably related to the radiotracer and of clinical concern.

After review of the safety data, SAEs and AEs confirmed to have been related to the radiotracer will be reported to the FDA and the appropriate regulatory committees at Yale. The study will be placed on hold until a determination is made as to whether the study may continue as written, if modifications are needed, or if the study will be discontinued.

Definitions

Adverse event (AE) means any untoward medical occurrence associated with the use of an intervention in humans, whether or not considered intervention-related (21 CFR 312.32 (a)).

An AE or suspected adverse reaction is considered "serious" (SAE) if, in the view of either the investigator or sponsor, it results in any of the following outcomes:

- death,
- a life-threatening adverse event,
- inpatient hospitalization or prolongation of existing hospitalization,
- a persistent or significant incapacity or substantial disruption of the ability to conduct normal life functions,
- a congenital anomaly/birth defect, or
- An important medical event that may not result in death, be life-threatening, or require hospitalization may be considered serious when, based upon appropriate medical judgment, they may jeopardize the participant and may require medical or surgical intervention to prevent one of the outcomes listed in this definition. Examples of such medical events include allergic bronchospasm requiring intensive treatment in an emergency room or at home, blood dyscrasias or convulsions that do not result in inpatient hospitalization, or the development of drug dependency or drug abuse.

HIC 2000030749

Severity

Adverse events will be graded according to [name grading scale, e.g. CTCAE v5.0]. For AEs not included in the protocol defined grading system, the following guidelines will be used to describe severity.

- Mild – Events require minimal or no treatment and do not interfere with the participant's daily activities.
- Moderate – Events result in a low level of inconvenience or concern with the therapeutic measures. Moderate events may cause some interference with functioning.

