- Severe – Events interrupt a participant's usual daily activity and may require systemic drug therapy or other treatment. Severe events are usually potentially life-threatening or incapacitating. Of note, the term "severe" does not necessarily equate to "serious".]

Relationship to Investigational Product

All AEs must have their relationship to study intervention assessed by the clinician who examines and evaluates the participant based on temporal relationship and his/her clinical judgment. The degree of certainty about causality will be graded using the categories below. In a clinical trial, the study product must always be suspect.

- Definitely Related – There is clear evidence to suggest a causal relationship, and other possible contributing factors can be ruled out. The clinical event, including an abnormal laboratory test result, occurs in a plausible time relationship to study intervention administration and cannot be explained by concurrent disease or other drugs or chemicals. The response to withdrawal of the study intervention (dechallenge) should be clinically plausible. The event must be pharmacologically or phenomenologically definitive, with use of a satisfactory rechallenge procedure if necessary.
- Probably Related – There is evidence to suggest a causal relationship, and the influence of other factors is unlikely. The clinical event, including an abnormal laboratory test result, occurs within a reasonable time after administration of the study intervention, is unlikely to be attributed to concurrent disease or other drugs or chemicals, and follows a clinically reasonable response on withdrawal (dechallenge). Rechallenge information is not required to fulfill this definition.
- Potentially Related – There is some evidence to suggest a causal relationship (e.g., the event occurred within a reasonable time after administration of the trial medication). However, other factors may have contributed to the event (e.g., the participant's clinical condition, other concomitant events). Although an AE may rate only as "possibly related" soon after discovery, it can be flagged as requiring more information and later be upgraded to "probably related" or "definitely related", as appropriate.

HIC 2000030749

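### The automatic stopping triggers count only radiotracer-related events, so an SAE attributed solely to microneurography brings reporting and discretionary review but no automatic hold

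*Combined protocol and SAP*

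**What the plan says.** Sections 6.2.3 and 7.12 carry the same rule. Either of two events stops the study:

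- an SAE in one or more subjects, "considered by the investigator to be possibly or probably related to the radiotracer";
- severe AEs in two or more subjects, "considered by the investigator to be possibly or probably related to the radiotracer and of clinical concern".

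The next paragraph sends SAEs and AEs confirmed as tracer-related to the FDA and to institutional committees, and then says: "The study will be placed on hold until a determination is made as to whether the study may continue as written".

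Section 6.2.3 has two causality scales. The first rates each event against study procedures and agents together, and its top category is definite. The second concerns the investigational product, and its top category is Definitely Related: "There is clear evidence to suggest a causal relationship, and other possible contributing factors can be ruled out".

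Section 3.2.1 describes the microneurography risk. Paresthesia lasting 2 to 10 days is reported in less than 10%; "in less than 1% of all subjects paresthesia can persist for up to two months"; it resolves spontaneously. The same section sets controls: experienced operators, a search time under 60 minutes, single-use electrodes, sterile technique, and "No nerve site will be sampled more than once".

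For the tracer, sections 3.2.1 and 6.2.3 state that no adverse effects have been reported.

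**The concern.** The automatic rule covers the exposure for which the protocol reports no adverse effects. It omits the exposure for which the protocol quantifies an injury risk. Procedure attribution is collected under the first scale, but neither trigger uses it.

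What differs is the step after attribution. An SAE of persistent disability judged possibly or probably due to the tracer must stop the study. The same SAE judged due only to nerve recording need not stop anything, and recordings in other participants could go on while the case is considered.

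The wording has a second, smaller defect. Taken literally, a tracer event with the strongest causal rating does not meet either trigger.

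**Working it through.** The plan gives no operating characteristics for its stopping rule, so there is no figure to reproduce. The check is a reading of the rule, followed by arithmetic on what the fix could cost.

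**1. How a microneurography-only SAE counts.** Both triggers require attribution to the tracer. The event counts 0 toward trigger 1 (threshold 1) and 0 toward trigger 2 (threshold 2), however many subjects are affected. Planned exposure is 40 participants × 2 visits (4 and 5) = 80 recordings, before drop-out and repeats.

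**2. Whether the hold sentence fills the gap.** It does not name the tracer. But it follows the two tracer triggers and a sentence confined to tracer-related events, so it cannot fairly be read as a free-standing hold for any SAE.

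**3. The definite category.** Both scales in 6.2.3 place a category above probable. The triggers name only possible and probable.

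**4. Other routes for a microneurography SAE.**

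- UPIRSO reporting to the IRB (6.2.3): required if the event is unexpected, at least possibly related, and suggests greater risk than known. It is a report, not a hold.
- Investigator review of all AEs (6.2.3, 7.12): comes when each subject completes.
- Monthly review of any AE by the PET Center's internal board (6.2.3): no hold threshold is stated.
- Authority of the investigator, the HIC and others to suspend (6.2.3, 6.5.4, 7.11): a power, not a duty.
- Unacceptable risk as a ground for suspension (7.14): permissive wording.

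None of these is automatic.

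**5. False pauses if microneurography had its own hold.** Inputs: n = 40 (5.3.1), and lasting paresthesia in less than 1% of subjects (3.2.1), taken at its upper limit p = 0.01. Assumptions: all 40 are recorded, participants are independent, and ordinary 2 to 10 day paresthesia is not graded severe or classed as an SAE.

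- Expected number with lasting paresthesia: below 0.01 × 40 = 0.4. This is an expected count, not a ceiling.
- If no lasting case is graded severe or serious, the chance that known paresthesia causes a pause is 0.
- If every lasting case is graded severe and of clinical concern: P(2 or more subjects) = 1 − 0.99^40 − 40 × 0.01 × 0.99^39 = 1 − 0.669 − 0.270 = 0.061, so below 6.1%.
- If every lasting case is classed as an SAE, which is unlikely because it resolves: P(1 or more) = 1 − 0.99^40 = 0.331, so below 33.1%.

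**The case against.** A tracer-only trigger is a defensible choice. The tracer is the investigational product (6.1.1). Microneurography is established at the institution: section 5.1 lists three HIC protocols under which it was approved and a fourth under which it is in use. Section 3.2.1 adds controls, and the known harm is self-limiting. A lasting disability from nerve recording would probably meet all three UPIRSO criteria, since it would be unexpected against a risk described as resolving. The IRB would then have to be told, and the HIC can stop the study. Section 6.2.3 also says "In a clinical trial, the study product must always be suspect", so events on scan days may be rated possibly tracer-related.

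Most of this stands, and it is why the gap is small. It does not close the gap. Controls lower the chance of an event but do not say what follows one. A report to a body that may suspend is not a hold. The presumption against the study product has little purchase at visits 4 and 5, where no tracer is given. The 1 to 3 day safety call follows the PET scan only; the other stated call comes 1 to 2 weeks after study completion (6.3.6).

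A reader might infer that nothing in the plan could stop the study after a microneurography injury. The routes above show otherwise. A reader might also infer that definite tracer events were deliberately excluded. Nothing supports that, and an oversight is far more likely.

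**Conclusion.** The point holds in a limited form. No automatic hold follows an SAE attributed solely to microneurography, and the literal wording omits definite tracer events. Both follow from the text of 6.2.3 and 7.12 without any numerical assumption.

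The practical size is small. The documents give no rate of procedure SAEs, so the benefit of a trigger cannot be quantified; the 80 planned recordings measure exposure, not harm. The probabilities above describe only the cost of the fix, and they depend on how lasting paresthesia would be graded.

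Two wider readings should be avoided. Applying the 1% to each recording would raise the probabilities, but section 3.2.1 states the rate per subject. Extending the point to every invasive procedure would also go too far. Beyond microneurography and routine venous access, the only candidate is an arterial line, which is listed only in 6.3.5; the Visit 3 description in 5.1 names only an intravenous catheter.

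**What to change.** Make the same two edits in 6.2.3 and 7.12.

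(a) In the existing triggers, write: *possibly, probably or definitely related to the radiotracer*.

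(b) After the triggers, add a separate sentence: *Microneurography (or arterial-line placement, if used) will be placed on hold pending review if 1 or more subjects have an SAE, or 2 or more subjects have severe AEs of clinical concern, possibly, probably or definitely related to that procedure; other study visits may continue.*

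A separate sentence matters. If procedures were added inside the existing triggers, the lead-in would stop the whole study for an event confined to one procedure. PET visits can continue during a microneurography hold, because section 5.1 does not require the PET and MSNA visits to occur in sequence. FDA reporting stays specific to the tracer.

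Endpoints, sample size and analysis do not change. The cost is a possible short pause of one procedure. A long hold could lose some MSNA visits, because section 6.3 places all visits within 8 weeks. The edits can go into the next amendment as a low priority.
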